1.0 Background

Cigarette smoking significantly increases the risk of multiple cancers, accounting for more than 30% of all cancer deaths and 80% of deaths from lung cancer¹. Compared to whites, African Americans have lower cessation rates and are disproportionately burdened by lung cancer^{2,3}, underscoring the urgent need for improved smoking cessation strategies in these underserved groups. Personalizing standard care⁴ with biological data to enhance accuracy of lung cancer risk⁵ or measure speed of nicotine metabolism to inform pharmacotherapy choice⁶ is a promising, yet understudied, approach in low income minority smokers.

The Southern Community Cohort Study (SCCS) is comprised of adults who were ages 40-79 at cohort entry and who reside in twelve states throughout the southeastern US. The majority (86%) were enrolled at 71 CHCs, which continue to serve as study partners, with recruitment completed in 2009. In addition to annual passive follow up of the SCCS from 2008 to 2012 via linkage with national and state mortality and cancer registries, the entire surviving cohort was re-contacted to participate in a follow-up self or telephone administered survey, with a nearly 70% response rate. The follow-up survey elicited information on new health outcomes and updated information on exposures and lifestyle factors, including smoking. Smoking-related questions were added to the 3rd follow up in order to probe participants' motivation, use of quit aids, receipt of provider advice, quit attempts, and cessation.

[figure not shown]
Through the SCCS, genetic polymorphisms in cytochrome P450 2A6 (CYP2A6), a primary driver of metabolism of nicotine and carcinogenic tobacco-specific nitrosamines, have been found to predict lung cancer risk in African-American male smokers⁷. Additionally, it has been found that individuals who metabolize nicotine and nitrosamine more quickly, termed "fast/normal" metabolizers, have a 45% higher risk of lung cancer compared to so-called "slow" metabolizers⁸.

2.0 Rationale and Specific Aims

Biologically informed precision treatment could benefit smokers in several ways. Biological tailoring may increase the salience of messaging about smoking-related disease and advice to quit. This in turn could reduce the optimistic bias, a tendency to underestimate one's own health risk, which hinders cessation efforts⁹, thereby increasing motivation to quit. Data has demonstrated that the nicotine metabolite ratio (NMR), a biomarker reflecting CYP2A6 activity, can inform choice of smoking cessation pharmacotherapy, such that "fast/normal" metabolizers are twice as likely to quit smoking on varenicline compared to "slow" metabolizers⁶. Additionally, smokers who are presented results from a commercially available, gene-based lung cancer risk assessment, Respiragene, are more likely to undergo lung cancer screening¹⁰⁻¹³. Respiragene recipients were also more likely to use nicotine replacement therapy (NRT) and quit smoking^{5,14-16}. Though promising tools to help engage smokers in cessation treatment, these individual, biologically informed feedback interventions have not yet been studied in community smokers in the US.

Our overarching aim is to leverage the SCCS and the U54 Community Outreach Core Community Advisory Board (CAB) to guide the development of two precision care (PC) interventions for smoking cessation: PC-NMR and PC-Respiragene. Both will be tailored to attitudes and beliefs of low socioeconomic status (SES) community smokers in the southeastern US, where tobacco use prevalence is one of the highest in the country. PC is rooted in the PRIME Model of behavior change¹⁷⁻¹⁹, which reflects a multi-faceted view of motivation for tobacco cessation. We will assess feasibility of PC in SCCS participants who smoke and conduct a 3-arm randomized controlled trial (RCT) to determine preliminary estimates of PC interventions vs. standard guideline-based care (GBC) on engagement^{4,20}, smoking cessation, and likelihood of undergoing recommended lung cancer screening if eligible²¹. Our hypothesis is that, compared to GBC, PC participants will exhibit higher smoking cessation and lung cancer screening rates. These effects will be explained by lower optimistic bias, higher self-efficacy and motivation to quit, and use of proven quit aids (medication, behavior therapy via state quit line).

To accomplish our aim, daily smokers who are SCCS participants and providers at SCCS Community Health Centers (CHC), in Mississippi or Tennessee will be surveyed to assess their attitudes and beliefs about precision smoking treatment. Survey results will inform CAB-guided development of the PC study interventions. PC interventions will then be piloted in a RCT of up to 100 SCCS daily smokers willing to make a quit attempt with medication and be randomized 1:1:1 to PC-NMR, PC-Respiragene, or GBC and followed for 6 months. All RCT participants are referred to the shared TN/MS state quitline and provided the NCI “Clearing the Air” standard intervention.

An overview of Aims 1 and 2, which are now completed, is shown to the left.

Aim 1: Survey up to 1400 TN and MS SCCS smokers and up to 45 selected CHC providers to assess attitudes and beliefs on smoking-related health risk perceptions, precision smoking treatment, and willingness to engage in a smoking cessation trial of PC.

Aim 2: With continuous input from the CAB, develop two PC interventions, PC-NMR and PC-Respiragene, for use among diverse, low-socioeconomic status community smokers in the SCCS.

Aim 3: Conduct a 3-arm RCT to pilot PC interventions for feasibility and to determine preliminary estimates of biochemically-validated smoking cessation at 6 months vs. GBC. We hypothesize that, compared to GBC, PC participants will exhibit higher smoking cessation and lung cancer screening rates. (Illustration of Aim 3 is shown below on p. 8).

3.0 Animal Studies and Previous Human Studies

Our group has not performed prior animal or human studies related to the proposed PC interventions.

4.0 Inclusion/Exclusion Criteria

AIM 1:

Patient Inclusion Criteria: Eligible participants include adult (18 years of age or older) self-identified current smokers who are SCCS Participants.

Provider Inclusion Criteria: Eligible participants include independent providers at selected CHCs as provided by CHC CEOs.

AIM 3:

Inclusion Criteria: Eligible participants include adult (18 years of age or older) daily smokers (i.e., indicated they were smoking ≥ 5 cigarettes per day on most recent survey) who are SCCS participants and agreed to be contacted in the Aim 1 survey. Participants must have a stored blood sample with the

SCCS and an established PCP. Participants must agree to participate and be willing to accept a medication prescription for tobacco cessation. Participants must be eligible (i.e., no medical contraindications) to receive at least 1 non-nicotine FDA-approved smoking cessation medication (i.e., varenicline) and NRT. Smokers across the motivational spectrum (all levels of readiness to quit) are eligible.

Exclusion Criteria: Inability to give informed consent or participate due to serious psychiatric (e.g., psychosis, schizophrenia, hospitalization for psychiatric condition in the past 6 months) or cognitive disorder (e.g., dementia, that prevents them from completing study procedures); enrolled or scheduled to be enrolled in another smoking cessation program; no access to a telephone or inability to communicate by telephone; unable to speak and read English; history of seizures; pregnant or breastfeeding.

5.0 Enrollment/Randomization

For AIM 1 provider participants, we will first obtain name and contact information for CHC CEOs from the SCCS. CEOs for selected CHCs will be mailed an introductory letter directing them to an emailed REDCap survey, the purpose of which is to obtain, at the discretion of the CEO, CHC providers' names, credentials, and email addresses. This email will be re-sent 2 times at 2 week intervals in order to ensure maximum response rates. Using the obtained email addresses, we will email the AIM 1 provider REDCap survey, which assesses providers' current tobacco treatment practices as well as attitudes toward personalizing smoking cessation treatment. This email will be sent to non-responding providers 2 times at 2 week intervals in order to ensure maximum response rates.

For AIM 1 patient participants, we will use the well-established SCCS procedures for entry into, and follow-up within, the SCCS. Mailed packets will include a pre-addressed and postage-paid return envelope, with only the SCCS participant number for identification. The packets will also contain an introductory letter describing the research, and an AIM 1 questionnaire to complete. . To ensure maximum response rate, participants will be mailed up to three times;. Participants will mail back the questionnaire and, upon receipt of these items, will be considered potentially eligible for the AIM 3 pilot RCT.

Respondents to the AIM 1 survey who report that they have a PCP and who have an SCCS stored blood sample will be mailed an AIM 3 invitation letter and informed consent with a pre-paid return envelope. These patients will be screened for eligibility by phone and, for those providing verbal consent, given the AIM 3 baseline questionnaire by phone. Upon return of the signed written consent form, the participant's labs will be run using their stored blood. When these results are available, participants will be called and informed of their randomization assignment (PC-NMR, PC-Respiragene, GBC). The baseline questionnaire for the RCT will contain questions on lifestyle factors, readiness to quit, and smoking patterns as described below. Computer-assisted telephone interviewing will also be used for completion of study questionnaires by phone using the study call line; study staff will contact non-responders by mail or phone.

Eligible patients will be randomized according to a stratified permuted block randomization scheme. Stratification will be based on cigarettes per day. Randomization will be proceeded within strata according to a permuted block scheme with a block size, or balancing interval, varying randomly between 3 or 6 according to the outcome of a computer generated random number. This will ensure that the cumulative number of assignments to each treatment is in balance after making each block of assignments.

6.0 Study Procedures

Baseline Data Collection

For Aim 1, participants will be mailed a questionnaire and a postage-paid return envelope. The survey will assess current smoking behavior as well as attitudes toward smoking cessation, precision medical care, and participants' perceptions of health risk. This survey will be mailed up to 3 times.

Aim 1 and Aim 2 inform each other as outlined in Figure 1 below. Aim 3 is an RCT piloting the use of the behavioral and educational interventions developed in AIM 2 within a low-income population, a subset of our Aim 1 participants as described above.

Respiragene measurement

For Aim 3, participants will undergo Respiragene testing, a genetic test that assesses lung cancer risk. Respiragene can be run on stored blood samples from the SCCS. If blood is not available, saliva could be used as a back-up. Risk level is stratified as high, higher and highest risk based on genetic markers. The VUMC lab that has performed most of the SCCS analyses to date will perform the Respiragene analysis. Those in the Respiragene arm of the study will receive the results of their Respiragene lab test during their first quit attempt. All others will receive their results at the end of the study. This final results call will be offered to all participants around the Month 6 follow up..

Nicotine metabolite ratio (NMR) measurement

For Aim 3, participants will also undergo nicotine metabolite ratio (NMR) testing of stored biological samples (blood will be used when possible and is preferred; saliva can be used as a substitute). NMR testing helps to determine how quickly a participant's body breaks down nicotine, which will inform his or her provider about whether nicotine replacement therapy (NRT) or varenicline is more effective to help the participant quit smoking. Samples will be securely shipped to Canada for testing. Slow metabolizers will be defined by an NMR <0.31 and fast metabolizers will be defined by an NMR ≥ 0.31 ⁶. Those in the NMR arm of the study will receive the results of their NMR lab test and their medication will be selected based on their NMR status. At the end of the study, those who were not in the NMR arm will receive their NMR results. This final results call will be offered to all participants around the Month 6 follow up.

Medication provision and blinding

Guideline Based Care Group

All participants assigned to guideline based care (GBC) will be referred to the state quitline and will receive a smoking cessation intervention through the National Cancer Institute's (NCI) "Clearing the Air" program. Additionally, as part of clinical care, the primary care provider (PCP) will document guideline-based treatment recommendations and provide participants with prescriptions sufficient for a 3-month course of pharmacotherapy chosen at the clinical discretion of the provider. Written and verbal instructions will be provided to participants given medication to contact their primary provider and the research study staff (during regular business hours) to address any questions about medication. Participants will be instructed to call 911 if they believe they are having a medical emergency. GBC participants will also receive Respiragene and nicotine metabolite ratio (NMR) testing on their SCCS stored blood sample and will be informed of these results at the end of the study.

Respiragene Precision Care Group (PC-Respiragene)

All participants assigned to Respiragene precision care will receive guideline-based care, including a referral to the state quitline, as described above. Additionally, the PCP will have clinical decision support regarding the interpretation of the Respiragene test. Study staff will discuss results of the Respiragene test with the participant and the PCP will provide participants with prescriptions sufficient for a 3-month course of pharmacotherapy chosen at the clinical discretion of the provider based on guidelines relevant to differential health risks.

NMR Precision Care Group (PC-NMR)

All participants assigned to NMR precision care will receive guideline-based care, including a referral to the state quitline, as described above. Additionally, the PCP will have clinical decision support regarding the interpretation of NMR from the study team. Using the NMR data, the PCP will discuss

results with the participant and provide participants with prescriptions sufficient for a 3-month course of pharmacotherapy based on NMR results (NRT for “slow” metabolizers and non-nicotine smoking cessation medication (varenicline) for “fast/normal” metabolizers). Participants who do not wish to receive varenicline, may have the option of a higher nicotine patch dose that has been studied previously. In this previous study, there were no significant differences between treatment arms in the frequency of severe side effects and serious adverse events or blood pressure during treatment ($p > .10$).²²

Participants may receive prescriptions through their own pharmacies or through a mail order pharmacy.

Check-in phone calls

Study staff will call participants at approximately 2 weeks after the study results call, and again approximately 1- 2 months following the results call, to encourage medication adherence and assess self-reported tolerance. If additional communication is needed, a tobacco counselor can be available for extra calls.

Table 1: RCT Data Collection Table for Aim 3					
Follow up Assessments	B L	1 mo f/u	Informal Check-in (2)	3 mo f/u	6 mo f/u
Smoking status	X	X		X	X
Cigarettes per day	X	X		X	X
Health risk perceptions	X	X		X	X
Lung cancer screening	X	X		X	X
Notify of PC results*		X			X
Calls to support med		X	X	X	

Outcome assessment

Subject outcomes will be assessed via phone calls at approximately 1, 3, and 6 months, as shown in Table 1. At follow up, an RA who is separate from intervention staff will complete interviews assessing smoking behavior, medication use and self-reported side effects, patient health risk perceptions and attitudes toward the PC interventions, and whether the patient received a lung cancer screening. Participants reporting abstinence at six months will be mailed a standard salivary cotinine kit for biochemical validation of smoking abstinence, defined as ≤ 10 ng/ml.

adherence, tolerance					
CO-validated abstinence					X
*Participants in PC arms (Respiragene, NMR) notified of results; GBC participants are contacted to match for time					

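### Does tying the Respiragene result to a first quit attempt leave some PC-Respiragene participants uninformed until Month 6?

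*Combined protocol and SAP*

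**What the plan says.** The Respiragene paragraph of section 6.0 states: "Those in the Respiragene arm of the study will receive the results of their Respiragene lab test during their first quit attempt". It sets no quit date and gives no way of detecting an attempt. It defers everyone else's result to the end of the study and adds: "This final results call will be offered to all participants around the Month 6 follow up". The parallel NMR paragraph has no behavioural trigger: "Those in the NMR arm of the study will receive the results of their NMR lab test".

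Section 5.0 gives the sequence. Once written consent is returned, the participant's "labs will be run using their stored blood". Then: "When these results are available, participants will be called and informed of their randomization assignment (PC-NMR, PC-Respiragene, GBC"). The stated content of that call is the assignment.

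The PC-Respiragene description in section 6.0 says "Study staff will discuss results of the Respiragene test with the participant", and the same sentence goes on to the primary care provider's prescription. Check-in calls are counted from a study results call. Table 1 marks notification in the 1-month and 6-month columns, with the footnote "Participants in PC arms (Respiragene, NMR) notified of results; GBC participants are contacted to match for time".

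Section 4.0 accepts smokers at any level of readiness but requires willingness to take a cessation prescription. Section 2.0 describes trial participants as prepared to attempt quitting with medication. Section 10.0 makes feasibility the primary outcome and says the trial is not powered for cessation.

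**The concern.** Learning the Respiragene result is what PC-Respiragene adds to guideline-based care, since the choice of medication stays with the provider. If disclosure waits for a quit attempt, three problems follow.

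- Exposure to the intervention would depend on a post-randomisation behaviour in one arm only, which would dilute the as-randomised estimate against GBC.
- A participant not told before Month 6 could be counted either as a delivery failure or as handled per protocol. That matters when feasibility of administration is the question.
- GBC contacts could not be time-matched to an event with no definition.

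A related worry is order. Table 1 puts notification and the risk-perception assessment in the same 1-month column, with no stated sequence or time origin. Lower optimistic bias is one of the proposed explanations of the effect, so it matters whether risk perception was measured before or after the result was given.

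**Working it through.** The documents give no figure to reproduce on this point, so the check compares the texts and adds a small timing calculation.

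**Step 1. Set the places side by side.**

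| Place | What fixes the timing | Conditional on a quit attempt? |
|---|---|---|
| 6.0, Respiragene paragraph | first quit attempt, undefined | on a literal reading, yes |
| 6.0, NMR paragraph | none stated | no |
| 5.0, call after labs | availability of lab results (conveys assignment) | no |
| 6.0, PC-Respiragene description | none; joined to the prescription | no |
| 6.0, check-in calls | counted from the results call | no |
| Table 1 and footnote | 1-month column (and 6-month) | no |

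One sentence carries the condition, and even that sentence does not say that results are given only if an attempt occurs.

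**Step 2. Try the literal reading.** Let T be the date of the first attempt, in months. Two weeks is 14/30.4 = 0.46 month. Check-ins would fall at T + 0.46 and between T + 1 and T + 2. For a participant with no attempt T does not exist, so neither check-in can be scheduled, although the plan gives both to participants generally. The Table 1 footnote would also fail, because it has the PC arms notified without exception.

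**Step 3. Try the ordinary reading.** Take the first quit attempt to be the study treatment episode, which begins with the results discussion and the prescription. The check-ins can then be dated for everyone:

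- Results call at month 1: 1 + 0.46 = 1.46 months, then 1 + 1 = 2 to 1 + 2 = 3 months. Both lie between the 1- and 3-month follow-ups, as Table 1 orders its columns.
- Results call when labs are ready, taken as time zero (an assumption): 0.46 month, then 1 to 2 months. The first falls before the 1-month follow-up. Table 1 shows both check-ins in one column, so its order may be only schematic.

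The documents do not choose between these two, but neither needs a quit attempt to occur.

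**Step 4. Who waits until the end?** The deferral follows directly on the sentence about the Respiragene arm, so it covers people outside that arm. The NMR paragraph confirms this pattern by naming those not in the NMR arm, and the GBC description defers results for that group. The final call is offered to everyone because every participant has at least one result still undisclosed; for PC-Respiragene this is the NMR result. Nothing assigns that call to participants who made no attempt.

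**Step 5. Order within month 1.** The follow-up interview asks about medication use, side effects and attitudes toward the PC interventions, which makes most sense after the result has been given. An assistant separate from the intervention staff conducts it, so sharing a column does not mean sharing a call. Risk perception is measured again at 3 and 6 months. If notification happens by about month 1, at least two assessments follow it whatever the order at month 1.

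**Step 6. Size.** Up to 100 participants randomised 1:1:1 gives 100/3, about 33 per arm, and 1/33 = 3.0 percentage points of an arm's delivery share per participant. This is only a unit of measurement. Without a quit-attempt rate, no number of affected participants can be put against it.

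**The case for a change.** The best case for a change is that willingness to try is not an attempt, and section 4.0 expressly lets in smokers who are not ready. No sentence supplies the disclosure rule that the ordinary reading assumes. The section 5.0 call is said to convey the assignment, not the result, and the arm description gives no date. The engagement measures in section 10.0 (counselor, quitline, medication) do not record whether or when the result was delivered, and the named process measures do not either. The lag before results is also unknown: labs wait for signed consent, and for NMR "Samples will be securely shipped to Canada for testing". A pilot meant to inform a later trial has reason to know who received its intervention and when.

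Part of this stands. The term is undefined, the time origin of follow-up is unstated, and the order of notification and the 1-month interview has to be inferred.

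The rest carries less weight. The process measures are introduced as examples, so the list leaves room for a delivery count. Staff must know the date of the results call to place a check-in two weeks later, so it is reasonable to expect that the information will exist. The dilution argument needs one phrase to override every other description of the call, and it bears on estimates that the plan labels exploratory. Figure 2, the Aim 3 schematic, is not visible in the text reviewed, so it cannot be said that the whole plan is silent on sequence.

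**Conclusion.** No change to the plan is needed. The wording is ambiguous, but the passages can be read together without contradiction if the first quit attempt is the study treatment episode. The literal alternative conflicts with the plan's own check-in schedule and Table 1 footnote. What remains is missing detail of a kind that trial staff and analysts can settle sensibly: which call gives the result, when follow-up time starts, and whether notification comes before the 1-month interview. Writing these down would make the text tidier, but it would not correct a rule shown to give a wrong result.

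The effect on any estimate cannot be calculated from the documents, and the affected comparisons are exploratory in a trial not powered for them. This conclusion rests on two assumptions: that the results call is made to all PC-Respiragene participants, as the arm description and footnote indicate, and that participants are analysed in the arm to which they were randomised. It takes no position on when results ought to be disclosed.

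### Could the final results call, timed only loosely to Month 6, contaminate the 6-month outcomes?

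*Combined protocol and SAP*

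**What the plan says.** Section 6.0 has all trial participants tested with both Respiragene and NMR, but each precision-care arm hears only its own result early on. For Respiragene, "All others will receive their results at the end of the study". For NMR, "At the end of the study, those who were not in the NMR arm will receive their NMR results". Guideline-based care (GBC) participants have both tests and "will be informed of these results at the end of the study". The Respiragene and NMR paragraphs each then add the operational timing: "This final results call will be offered to all participants around the Month 6 follow up".

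Table 1 marks the row "Notify of PC results" at 1 month and at 6 months. The 6-month column also holds smoking status, cigarettes per day, health risk perceptions, lung cancer screening and validated abstinence. Under the outcome assessment heading, a research assistant who is not part of the intervention staff conducts the interviews, which cover smoking, medication use, screening and "patient health risk perceptions and attitudes toward the PC interventions". Validation comes later: "Participants reporting abstinence at six months will be mailed a standard salivary cotinine kit for biochemical validation of smoking abstinence". No return deadline is given for the kit.

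Section 10.0 makes feasibility the primary outcome, says the trial is not powered for cessation, and labels the cessation and screening hypotheses exploratory.

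**The concern.** Telling smokers their biological results is the experimental ingredient. Section 2.0 expects higher cessation and screening in the precision-care arms and adds: "These effects will be explained by lower optimistic bias, higher self-efficacy and motivation to quit". If the last call came before the 6-month interview, GBC participants would already have heard both results when asked about risk perceptions and smoking, and each precision-care arm would have heard the other arm's test. The contrast with GBC could then shrink. This is most plausible for PC-Respiragene, because GBC would also have heard the lung cancer risk test. For PC-NMR against GBC the direction is unclear, because both arms would be hearing Respiragene for the first time.

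Interviewing first does not settle everything. The saliva kit goes out only after abstinence is reported, so a results call at the close of the Month 6 contact could still come before the sample. Month 6 is the only biochemically validated time point, and the validated estimate against GBC is a stated goal of Aim 3.

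**Working it through.** The plan states no figure on this point to reproduce. The check is of sequence, followed by a count of who is exposed.

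**1. What each statement implies about order.**
- The Respiragene, NMR and GBC paragraphs of Section 6.0 put the withheld results at the end of the study, and the call is described as final. These point to disclosure last.
- Section 2.0 follows participants for 6 months, and Table 1 has no outcome contact after Month 6. Section 11.0 mentions about 12 months, so the end of the study is not perfectly defined. Under either length, though, the end does not fall before the Month 6 interview.
- The Month 6 timing sentence is loose enough to allow a call slightly before or after the interview. It is the only wording that leaves the order open.
- Table 1 lists activities by visit and orders nothing within a column. Its 1-month column also holds both notification and outcomes. A shared 6-month column is therefore no evidence that disclosure comes first.

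**2. The possible sequences.**
- *Call after interview and sample:* no 6-month outcome can be affected.
- *Call after interview, before sample:* self-reported smoking, risk perceptions, attitudes and screening are already recorded. Only participants who have reported abstinence can be affected, through kit return or smoking before sampling. The validated count cannot exceed the number who had already reported abstinence.
- *Call before interview:* all 6-month outcomes are open to influence. This requires staff to give final, end-of-study results before the last assessment, against the ordinary sense of the text.

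**3. Exposure.** Tests known before the call: GBC 0, PC-NMR 1, PC-Respiragene 1. After it: 2 in every arm. New results heard: 2 − 0 = 2, 2 − 1 = 1 and 2 − 1 = 1. At the maximum of 100 randomised 1:1:1, each arm has 100/3 = 33.3.
- First hearing Respiragene in this call (GBC and PC-NMR): 2 × 33.3 = 66.7, at most about 67.
- First hearing NMR in this call (GBC and PC-Respiragene): 2 × 33.3 = 66.7, at most about 67.

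These totals would be the same if every call came after the sample. They count who hears a result, not who hears it too early, so they do not measure bias.

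**4. Scale.** One participant whose 6-month status changed would move an arm's rate by 1/33.3 = 3.0 percentage points. How many, if any, would change cannot be derived from the documents.

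**5. Outcomes at risk.** The engagement measures in Section 10.0 are contact with the counselor, contact with the quitline and use of medication. The prescriptions cover 3 months and the support calls fall within about 2 months of the first results call. If treatment starts soon after that call, most engagement has accrued before Month 6. Risk perceptions are also measured at 1 and 3 months, and Section 10.0 lists neither them nor a mediation analysis for Aim 3.

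**The case for a change.** The best case for a change is that the gap is real and cheap to close. No sentence sets the order, the end of the study is undefined given 6 months in one section and about 12 in another, and the separate research assistant governs who interviews rather than when results are given. The saliva gap survives even if staff always interview first. A sentence tying the call to completed outcomes would protect the only validated time point.

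The textual part stands: the order is implied, not written, and a call could precede the sample. The consequence does not follow. Nothing in the documents shows that hearing a result after reporting abstinence alters kit return or smoking in the days before sampling, and no direction can be given for either. Separating the interviewer from intervention staff fixes no order, but it makes it less likely that disclosure is casually folded into the interview.

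Nor is the remedy free. A kit-return window would have to be created and tracked, and reported abstainers would need a further contact, with some chance of losing them before they receive promised results.

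**Conclusion.** No change follows. This is a missing operational detail with an obvious sensible reading: interview at Month 6, then disclose. Under that reading the 6-month self-reports are untouched, and the one remaining exposure is a call that falls between the interview and the saliva sample. It is confined to reported abstainers, cannot add to them, and has unknown direction and undeterminable size; each altered status would be worth about 3 percentage points in an arm of 33.

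The estimate concerned is preliminary. Section 10.0 lists validated cessation among the Aim 3 estimates but treats the between-arm hypothesis as exploratory and unpowered, with feasibility as the primary outcome. A pilot run as written would still support sound conclusions about feasibility.

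This rests on two assumptions: that staff take end-of-study disclosure to mean after the Month 6 interview, and that cessation results are reported as preliminary. If many results calls were in fact made before the interview, the 6-month risk-perception and cessation contrasts, particularly PC-Respiragene against GBC, would need to be read with that in mind.
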